1. PURPOSE OF STUDY

To demonstrate that a multidisciplinary team intervention using pre-specified standard of care medication dosing guided by ICD-derived data will increase the rate of change in Guideline Directed Medical Therapy (GDMT) medication dosing in the intervention group compared to usual care at 6 months in cardiomyopathy patients who have received an ICD for primary prevention.

2. BACKGROUND AND RATIONALE

Most patients with ischemic and non-ischemic cardiomyopathies do not receive optimal Guideline Directed Medical Therapy (GDMT) at the time of ICD implantation. Our data from the Rochester ICD Registry show that >60% of patients who are implanted with an ICD do not receive all guideline-recommended medications for heart failure (HF) at the time of device implantation and >90% do not receive an optimal dose of the recommended drugs¹. Furthermore, most HF patients do not receive prescription for a regular exercise program, despite the fact that activity was shown to be associated with improved morbidity and mortality in this population². Accordingly, there is a ~30% higher relative risk of adjusted mortality rate for patients not on GDMT³. In addition, the relatively low rates of patient activation and engagement in their care is associated with reduced outcomes and increased cost of care⁴.

Current medical management regimens are limited due to the fact that individual continuous functional and physiologic data are not available to the patient's health care providers, leading to reduced rates of guideline-directed medications, dose adjustments, and lack of appropriate exercise prescription. Physiologic and functional data from Cardiac Implantable Electronic Devices (CIEDs), including information on heart rate, activity, and fluid status derived from the OptiVol monitor, together with a concurrent patient engagement strategy through remote interactions, can be used to optimize the medical management of HF patients implanted with an ICD.

We hypothesize that continuous use of the standard CIED functional and physiologic data currently available to clinicians, integrated in the OptiVol-Monitor algorithm (Medtronic) and additional device features, can be used by an active remote multidisciplinary team directed GDMT to optimize medical management in patients with ischemic and non-ischemic cardiomyopathy (NICM) who have an implanted ICD.

We will show that the incorporation of Cardiac Compass data with pre-specified medication

regimens will result in optimization of GDMT medications compared to usual care and we will demonstrate the safety and utility of using CIED data for patient management. Furthermore, we would like to provide evidence that remote interactions, encouraging patient engagement via virtual visits and mobile device based quality of life questionnaires, can be used to improve functional and clinical outcomes in heart failure patients.

We chose to focus this pilot study on both ischemic and non-ischemic cardiomyopathy since patients in both groups have potential for improvement following medical optimization.

Objectives

To demonstrate that a multidisciplinary team intervention (see administrative organization section) using pre-specified medication dosing standards guided by CIED-derived data will increase the rate of change in GDMT medication dosing in the intervention group compared to usual care at 6 months in cardiomyopathy patients who have received an ICD (Medtronic) for primary prevention.

The secondary objectives are:

- 1) To characterize the correlation between Cardiac Compass-guided optimization and improved functional capacity and activity
- 2) To show that ICD-derived physiologic data, including arrhythmia and activity, are associated with clinical outcomes.
- 3) To validate a personalized framework for optimizing GDMT based medication dosing using time-dependent CIED and wearable sensor derived physiologic and functional data.
- 4) To characterize the correlation between wearable wristband sensors derived activity data and functional capacity and show that activity is associated with improved clinical outcomes.
- 5) Characterize health care utilization, defined as unplanned clinic visits, emergency department utilization, and hospitalization between CIED guided GDMT and usual care.
- 6) To develop a risk stratification scheme for adverse events within the total study population using time-dependent CIED and wearable sensor-derived physiologic and functional data.
- 7) To demonstrate that remote monitoring with a concurrent patient engagement strategy, using optional journal entries, is associated with improved clinical and functional outcomes and reduced health care utilization.
- 7) Quality of life (measured by Kansas City Cardiomyopathy Questionnaire) from enrollment to 6 months.

3. ADMINISTRATIVE ORGANIZATION

The study will take place at the University of Rochester Medical Center facilities. The investigators are both within the Department of Medicine-Cardiology. The PI and Investigators will lead the study and be responsible for study execution, safety, and data analysis. A Project manager, a Registered Nurse and Research Coordinators will have an active role throughout the study process.

4. STUDY DESIGN

The study is a randomized pilot clinical trial. The Coordination and Data Center (CDC) is at the University of Rochester. Each site will directly interface with the subjects for activities such as consent, testing, study team virtual and in person-visits.

The study will enroll approximately 30 subjects with ischemic and non-ischemic cardiomyopathy previously implanted with an ICD for primary prevention of sudden cardiac death. Subjects are followed for 6 months. Clinical, functional, and digital biomarker data will be captured related to: activity, heart rate, blood pressure, weight, blood biomarker BNP, quality of life status, and clinical events. Electronic health records will be monitored for 12-month period to collect/record study data.

Study data will be entered by site staff using a web-based data entry system at the University of Rochester for data management, analysis, and coordination of logistics.

The study duration is 2.0 years: including an estimated 3-month initiation phase; an estimated 8-month enrollment phase; and an estimated 6-month follow-up phase; with subsequent data analysis.

Primary Endpoint

The primary outcome of this study is the rate of change in medical management with beta-blockers, diuretics and Sacubitril/Valsartan (defined as initiation, termination, switch, or dosing adjustment) in the intervention group compared to usual care at 6 months.

Secondary outcomes

- Recurrent changes to medication type and dosing reflecting ongoing personalized optimization.
- Mean changes in functional status (measured by 6-minute walk distance) in the intervention vs. control groups.
- Percentage change in average daily activity level between the first month following discharge and the last month of the study (6th month) will be compared between intervention and control groups.
- Quality of life (measured by Kansas City Cardiomyopathy Questionnaire) from index discharge to 6 months after discharge in the intervention vs. control groups.
- Healthcare utilization as determined by unplanned office visits and hospitalizations.
- Cardiac hospitalizations and all-cause mortality.
- Laboratory biomarkers.

Screening

Potential subjects will be screened using electronic records to ascertain prior ICD implantation per inclusion/exclusion criteria. The potential subject's health care provider will be contacted for permission to approach the patient for further screening and if eligible, obtain consent.

Patients are randomized 2:1 into:

An Intervention Group

The clinical management of the intervention group will be comprised of the following:

- A study care-team, comprised of a Cardiologist, an Electrophysiologist, a Registered Nurse, and study coordinator who will receive monthly physiologic and functional reports derived from Medtronic CIEDs incorporating Cardiac Compass and OptiVol monitoring.

- The study team will also be provided with patient-specific data derived from patient reported outcomes that include symptoms, quality of life scores, and PROMIS data if available. PROMIS®, a tool developed for use by the National Institutes of Health provides quality of life data, and is part of standard clinical care at the University of Rochester Medical Center Cardiology Department for patients. This is a survey patients have the option of filling out at clinic visits and available through the electronic medical record.
- The Datos app platform will be used to conduct a separate Quality of Life study survey and weekly e-survey REDCap may also be used as an additional resource..
- A pre-specified management regimen based on standard clinical practice will be provided to the study team in which medical management including medication dosing (focusing on beta-blockers and diuretics) will be monitored and modified using CIED and OptiVol data (see Figure 1 and footnote* at end of document). This is based on current and accepted clinical practice.
- The study team will contact the patients on a monthly basis for 4 monthly virtual visits. Based on CIED and patient engagement data, the study team will adjust medications and dosages, and optimize activity/ exercise steps. All medication changes resulting from the virtual visits will be updated in the subject's electronic medical record and communicated by medical chart messaging or URMC email based on the patient physician's preference.
- All study team contacts with the patients will be virtual, using telecommunication or E-communication. These options include URMC approved Zoom portal (currently used for URMC telemedicine clinical care), phone, or email. If the telemedicine call (preferred method) is disconnected, phone or email will be utilized. These e-communications will occur using an existing HIPAA compliant platform to improve efficiency, patient engagement, and reduce study costs while preserving data quality.
- In-person clinic research visits will be scheduled at 3 and 6 months, if feasible (if in-person visit is not feasible, Zoom or telephone visit will be conducted). Medication changes may occur based upon study physician judgement, assessment including NYHA class, in- person device interrogation, and patient reported symptoms.
- Garmin wearable wristband sensor data, such as number of steps, heart rate, and oxygen saturation, is passively captured and not used for patient management.
- CIED functional and physiologic data, as well the OptiVol monitor information and wristband sensor data will be captured in the study digital biomarker core-lab to better understand risk stratification in the total study population following study completion (see secondary aims above).

A Conventional Management Control Group

The clinical management of the control group will be comprised of the following:

- In-person clinic research visit, if feasible (if in-person visit is not feasible, Zoom or telephone visit will be conducted) will be scheduled at 3 and 6 months, similar to the intervention group. The 3 and 6-month visit includes: in-person device interrogation, NYHA class, any changes to medication or new events.
- To control for patient contact, patients in the conventional management group will receive 4 monthly virtual visits from the same study team. The study team will ask questions about symptoms, changes in activity levels, medication changes by their non-study

physician, and any adverse events. The study team however will not be provided with any patient specific Optivol data, survey results or PROMIS® data.

- CIED functional and physiologic data, as well the OptiVol monitor information and wearable wristband sensor data, for the control group will be captured in the study digital biomarker core-lab for the development of a risk stratification scheme in the total study population following study completion (see secondary aims above).
- The non-study physician will receive CIED/OptiVol data (as in usual care) and its use and the management strategy will be left to his/her discretion.
- The wearable wristband sensor data is passively captured and not used for patient management. Only the data currently available in remote monitoring from the ICD is being used which is same as current usual care.

Addition or removal of heart failure medications and changes in medication dosage will be left to the discretion of the treating physician. Upon completion of 6 month follow up the subjects will no longer require study visits and will return study equipment. We plan to collect study data from the electronic health record through 12 months at which time no further data will be collected.

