7. STUDY PROCEDURES

After consent, subjects will undergo/agree to the following study-related procedures (Consent and Enrollment may be done at separate visits):

- Garmin wearable wristband is provided for daily wear. Subjects should wear the wristband as often as possible. Subjects will return the Garmin wristband at 6 months.
- Quality of life questionnaire: KCCQ and a 3-question weekly electronic survey (e-survey) will be completed via the commercially-available Datos app platform. The survey

asks questions about how you are feeling, have you felt any symptoms, and the quality of your health status. The KCCQ should take 10 minutes to complete and the 3-question weekly e-survey should take 3 minutes to complete. Research staff will follow up with subject if weekly e-survey has not been completed for 2 weeks. REDCap may also be used as an alternative.

- Electronic medical record data regarding clinical history, medications, device implantation, and follow-up data will be collected for 12-month period.
- PROMIS data collected from medical record for 12 months, ICD data, medications, and other office visits/ hospitalizations/ unplanned visits standard of care will be available for chart review.
- Will participate in virtual visits, with phone visits occurring in the event a virtual visit is not possible. For those subjects in the intervention group, medications will be adjusted to optimize to medical guidelines; for those in the control group, no medications will be adjusted, but the subject will have the opportunity to share any changes in their medical status and any questions for the study staff. The control group will only receive their usual care and will not have their medications optimized by the research team. Visit time is approximately 30 minutes.
- Virtual Visit Overview with Subjects: Study staff will provide basic instruction to the subject on the use of Zoom. Study staff will show subject an example of a Zoom virtual visit to help them better understand the Zoom program before the first monthly virtual visit. Subjects will be invited, via e-mail link, to the Zoom meeting from the URMC HIPAA secured Zoom portal. They will then click on the invite link and will be directly connected with the study staff member. The Zoom Help Center (<https://support.zoom.us/hc/en-us>) may also be used as an online resource to help troubleshoot the virtual visit.

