 - Intervention group: Physical exam, NYHA class, 6-minute walk test, KCCQ, clinical and adverse events.
 - Control group: office visit for device interrogation, medical record review, report any changes in standard care. NYHA class, perform 6-minute walk test and KCCQ.

The CIED and Garmin wearable wristband physiologic (activity, heart rate, oxygen saturation) and functional data will be continuously captured by the study's core lab for all patients throughout follow-up. The Garmin Wristband sensor data will not be used for intervention. The

lab/data capturing process is HIPAA compliant and Garmin wristband is identified through a study ID number and patient name is not registered into with wristband.

Timeline	Consent/ Enrollment (may be separate visits)	Performed Weekly	1m +- 7d	2m +- 7d	3m +- 7d	4m +- 7d	5m +- 7d	6m - 7d/+14d	Thru Month 12 Chart Review No Visits
Informed Consent	✓								
Randomization	✓								
Medical History	✓								✓
Vital Signs: BP, weight, RR	✓				✓			✓	
Review Inclusion/Exclusion Criteria	✓								
Medication List	✓		✓	✓	✓	✓	✓	✓	✓
Blood Sample Repository: Optional	✓								
Remote CIED data acquisition	✓	Data Acquired remotely throughout study							
Remote Wearable data (Garmin) acquisition	✓	Data Acquired remotely throughout study							
QOL: KCCQ	✓							✓	
Weekly E-Survey	✓	✓							
6MWT	✓							✓	
Virtual Visit	✓		✓	✓		✓	✓		
In-person Clinic Visit: Physical Exam NYHA Class CEID Interrogation	✓				✓			✓	

Medication Optimization – Management Regimen

The clinical research team managing the intervention group will follow standard clinical discretion in adjusting medications as appropriate and will use the medication flowchart (Figure 1) that includes considering the clinical physiologic data that is available in ICD devices and used clinically.

[figure not shown]
The medication adjustment flowchart reminds clinicians to consider any device data such as heart rates and activity etc. as well as patient reported outcomes to optimize medication dosing to meet guideline directed medical therapy which is associated with long term survival benefit.

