17. DATA ANALYSIS PLAN

Statistical Methods

Primary Statistical Hypothesis

To test the hypothesis that a multidisciplinary team intervention using pre-specified medication

dosing regimens guided by Cardiac Compass-Optivol data will increase the rate of change in beta-blocker and/or diuretic prescription (defined as initiation, termination, or dose adjustment) in the intervention group compared to usual care at 6 months.

Statistical Test Method and Sample Size Considerations

The primary outcome of this study is the rate of change in medical optimization (changes in heart failure medications and dosing) guided by CIED physiologic and patient engagement app data that are used together with pre-specified medication dosing regimens over 6 months. The rate of change in HF medications (beta-blocker, diuretic, and Sacubitril/Valsartan) will be compared between the multidisciplinary team intervention guided by CIED physiologic digital data group and usual care control group using chi-square analysis. We estimate that the rate of medication change will be 10% in the conventional group based on our URMC ICD database, as compared to 60% in the intervention group. Accordingly, a sample of approximately 30 patients will be required to provide a power of 80% and a 2-sided alpha of 0.05, accounting for 10% drop out rate. The comparison of the rate of recurrent medication adjustments between the two study groups will be assessed using negative binomial regression analysis and is expected to result in greater than 80% power (possibly 99%) based on the expected rate of multiple medical changes (at the monthly virtual visits) in the intervention group.

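### The primary endpoint counts medication changes without direction, so a significant result alone supports more changes, not optimization of guideline-directed therapy

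*Combined protocol and SAP*

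**What the plan says.** Section 4 (Primary Endpoint) counts any change in three drug classes, "defined as initiation, termination, switch, or dosing adjustment". Section 17 (Primary Statistical Hypothesis) uses a slightly shorter list, "defined as initiation, termination, or dose adjustment". Neither gives a direction.

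The formal objective in Section 2 is that the intervention "will increase the rate of change in GDMT medication dosing in the intervention group compared to usual care at 6 months". Section 1 and the hypothesis in Section 17 are worded the same way in substance.

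Two other places go further:
- Section 2 says the trial will show that its approach "will result in optimization of GDMT medications compared to usual care".
- Section 17 opens its test description with "The primary outcome of this study is the rate of change in medical optimization (changes in heart failure medications and dosing", which treats change and optimization as one thing.

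Section 7 describes the purpose of the medication flowchart as to "optimize medication dosing to meet guideline directed medical therapy which is associated with long term survival benefit".

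The secondary outcome on recurrent changes is also a count without direction. The remaining secondary outcomes are walk distance, activity, quality of life, healthcare utilization, cardiac hospitalization and mortality, and laboratory biomarkers. None records direction of change or dose attained.

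**The concern.** Section 2 describes the clinical problem as patients who lack recommended drugs or an optimal dose of them. A result that answers that problem has to show movement toward recommended therapy. The endpoint cannot separate such movement from a stop, a reduction, a switch, or an increase that is later reversed.

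The study team prescribes in the intervention arm, while in control it does not ("for those in the control group, no medications will be adjusted" by that team). More changes of some kind are therefore expected wherever the intervention is delivered. What is at stake is the sentence written at the end of the trial: on the plan's own labels, a significant chi-square would be reported as optimization, and the primary data alone would not support that.

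**Working it through.** **Inputs.** From Section 17: 10% control, 60% intervention, chi-square, two-sided alpha 0.05, 80% power, 10% dropout, about 30 patients. From Section 4: 2:1 allocation. Thirty enrolled less 10% leaves 27 evaluable, or 18 intervention and 9 control.

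**The plan's own figure.** The normal formula for two proportions at 2:1, with no continuity correction, uses a pooled rate of (0.10 + 2 × 0.60)/3 = 0.433. The control-arm size is

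[1.96 × √(0.433 × 0.567 × 1.5) + 0.842 × √(0.10 × 0.90 + 0.60 × 0.40/2)]² / 0.50² = 9.9, rounded up to 10.

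That gives 10 + 20 = 30 evaluable (power 80.4%), or 30/0.9 = 33.3, so 34 enrolled. Summing exact binomial probabilities over all tables at 18 and 9 gives 78.9% power for the uncorrected chi-square. About 30 is therefore compatible with the stated inputs, and this point does not turn on the sample size.

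**Can the primary succeed with no difference in optimization?** Assume that 10% of patients in each arm have an optimizing change, and that the rest of the 60% in the intervention arm have only other changes. By the same exact enumeration at 18 and 9:

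| Test | Rates | Significant |
|---|---|---|
| Any change (planned primary) | 60% v 10% | 78.9% |
| Optimizing change only | 10% v 10% | 4.1% |

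The planned test cannot tell this case from one in which every change is optimizing.

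**How much does direction matter in less extreme cases?** Let s be the share of intervention changers (patients, not changes) with at least one upward change. The rate tested is 0.60 × s, with control kept at 10%, so every control changer counts as upward.

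| s | Intervention rate | Chi-square on upward change significant |
|---|---|---|
| 100% | 60% | 78.9% |
| 87.5% | 52.5% | 66.7% |
| 75% | 45% | 51.9% |
| 50% | 30% | 20.5% |

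The documents give no value of s. Its link to the share of changes depends on how many changes each patient has. If half of all changes are upward and changes are independent, then s = 1 − 0.5ᵏ for k changes per changer: 50% for k = 1, 75% for k = 2 and 87.5% for k = 3. Section 17 expects multiple changes at the monthly visits, so the one-change row is the low end. If control is thinned in the same way, the s = 50% row becomes 30% v 5%, significant 31% of the time.

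**Can direction be recovered?** Yes. The schedule of assessments in Section 7 records the medication list at enrollment, at months 1 to 6 and through chart review to month 12. No analysis of direction or dose is planned from it.

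**The case against.** The strongest reply is that the endpoint does what the formal text asks. Purpose, primary objective and hypothesis all speak of a higher rate of change, and the endpoint measures that. This stands: a reader might infer that the endpoint fails its objective, and it does not. The gap lies between the count and the word optimization in Sections 2 and 17.

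A reader might also infer that the trial could plausibly be positive on stops and reductions alone. The flowchart in Section 7 does not suggest this. Its beta-blocker rules name only an increase or no change, its diuretic rules are triggered by increased volume, and no listed rule calls for a stop. Clinical discretion covers all adjustments and no listed rule names Sacubitril/Valsartan, so the mix of changes is open. The flowchart also governs treatment, not how the endpoint is scored.

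A third tempting reading is that the arm difference is purely mechanical. Prescribing by the team is the intervention under test. Treating physicians of control patients receive device data and may change drugs (Section 4), so that reading is too strong.

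It is also fair to say that upward is not the same as optimizing. A reduction can be good individual care, a switch has no inherent direction, and diuretic changes follow volume status and symptoms. This stands and shapes the fix. Walk distance, quality of life and clinical events bear on whether patients benefited, but not on whether doses moved toward guideline therapy.

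**Conclusion.** The point holds as one of interpretation. The primary comparison is a valid test of whether the intervention produces more medication changes. Alone it cannot support a claim of optimization, and no other planned outcome measures direction or attained dose.

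The size is shown by the equal-optimization case: 78.9% v about 4%, on assumed rates. In the intermediate cases the chance of significance on upward change runs from 66.7% down to 20.5%, depending on a share of patients that the documents do not give. The 20.5% should not be read as what follows when half of the changes are upward. It needs exactly one change per changer and every control change counted as upward.

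**What to change.** Keep the primary endpoint and state that a significant result will be worded as more medication changes. Use one list of counted changes in Sections 4 and 17, since switch appears only in Section 4. Then pre-specify two additions:

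1. **A table by arm** of every counted change as initiation, increase, decrease, termination or switch, with each drug class separate. Diuretic changes are described but not scored as toward or away from a target.
2. **One supportive outcome**: change from baseline to 6 months in percent of target dose for beta-blocker and Sacubitril/Valsartan, compared by ANCOVA with the baseline value as covariate. The target-dose reference must be fixed before analysis. The protocol's drug dosage table could serve if it gives targets for these drugs. It is mentioned only in a beta-blocker rule and its content is not visible in the text reviewed. State how patients for whom a drug is not indicated or not tolerated are scored.

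Base any statement about optimization on these two items, and not on the primary count.

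The cost is SAP wording and dose coding of medication lists already collected, with no new visits or patients. The downside is low precision for the supportive outcome at about 30 patients, so it should be reported as an estimate with its confidence interval.

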4.1. SUBJECT POPULATION

Approximately 30 subjects total will be enrolled in this study following a 2:1 ratio (intervention: control). The study will be conducted at the University of Rochester Medical Center. Over 250 patients are newly implanted with a defibrillator per year and over 1,000 patients are followed within the system.

- Gender and Age of Subjects: Male and female subjects aged 18 years to 85 years. We expect to enroll about 25% women.
- Racial and Ethnic Origin: There are no restrictions on race or ethnicity in this study. We expect to enroll about 25% minority subjects.

Inclusion Criteria

- 18 to 85 years of age on the date of randomization
- ICD implantation for primary prevention in patients with ischemic and non-ischemic cardiomyopathy ≥ 3 calendar months from date of enrollment
- SMART Phone or tablet with Bluetooth capability with internet access
- No other identifiable reversible cause explaining the left ventricular dysfunction

Exclusion Criteria

- CRT implanted.
- LVEF $> 45\%$ in the last echocardiogram or other clinic imaging performed.
- Medtronic device generator and/or device components not implanted
- Unstable clinical condition, life threatening arrhythmia
- Heart failure hospitalization within the preceding 3 calendar months
- Cognitive impairment
- Severe renal dysfunction (eGFR < 30 ml/min/m²)

- Serious known concomitant disease with a life expectancy of < 12 calendar months
- Non-ambulatory NYHA class IV
- Pregnancy

Inclusion of Vulnerable Populations:

- Vulnerable populations: Women of childbearing potential are included if they are currently on the medications to be optimized (beta-blockers, diuretics and Sacubitril/Valsartan).

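### Activity and KCCQ are timed from a discharge the trial does not define, the activity source is not named, and section 17 gives no analysis for activity, KCCQ or 6-minute walk distance

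*Combined protocol and SAP*

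**What the plan says.** The secondary outcomes in section 4 include:

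- activity: "Percentage change in average daily activity level between the first month following discharge and the last month of the study (6th month"), compared between the groups;
- KCCQ: "from index discharge to 6 months after discharge in the intervention vs. control groups";
- walk distance: "Mean changes in functional status (measured by 6-minute walk distance) in the intervention vs. control groups".

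The Objectives in section 2 time KCCQ differently: "Quality of life (measured by Kansas City Cardiomyopathy Questionnaire) from enrollment to 6 months". The Follow-up Schedule and schedule table in section 7 agree with the Objectives. Visits are counted from enrolment, and KCCQ and the 6-minute walk are done at enrolment and month 6.

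Section 4.1 requires "ICD implantation for primary prevention in patients with ischemic and non-ischemic cardiomyopathy ≥ 3 calendar months from date of enrollment" and excludes "Heart failure hospitalization within the preceding 3 calendar months".

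Activity is recorded by two devices in both arms. One objective is to show that "ICD-derived physiologic data, including arrhythmia and activity, are associated with clinical outcomes"; another concerns "wearable wristband sensors derived activity data and functional capacity".

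Section 17 names a chi-square test for the medication-change rate and negative binomial regression for recurrent adjustments. It names no other method.

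**The concern.** A secondary outcome needs a start point, a data source and an analysis. Activity lacks all three. KCCQ has two conflicting start points and no analysis. Walk distance has a summary measure (mean change) but no stated comparison.

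What is at stake is the credibility of three between-group comparisons. The baseline month for activity has to be reinterpreted by whoever does the analysis. The choice between two activity streams, and the choice of model for all three outcomes, could be made after the data are seen. Precision is also at stake: baseline walk distance and KCCQ are already collected, and the plan does not say that they will be used for adjustment.

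**Working it through.** **Step 1: which discharge could be meant?** As a time point, the term occurs only in the activity and KCCQ bullets of section 4.

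- *Heart failure discharge.* An admission in the 3 months before entry is an exclusion, so any such discharge lies about 3 months or more before enrolment.
- *Implant discharge.* Implant is at least 3 months before enrolment. Assuming a short stay, discharge is at about study month −3 or earlier.

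On either reading, six months after discharge is study month −3 + 6 = 3 or earlier. KCCQ is collected at enrolment and month 6 only, so the KCCQ bullet fits neither reading. It fits enrolment, as the Objectives and schedule say.

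Activity ends at study month 6 whatever the anchor. On the implant reading its baseline month ends at about −3 + 1 = −2 or earlier. That is before the wristband is issued (enrolment visit, section 7), so only stored ICD data could supply it. The protocol does not say whether such data can be retrieved. The interval from discharge to month 6 would be about 3 + 6 = 9 months or longer, and would vary by patient.

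**Step 2: which device?** Three places lean towards the ICD: the first secondary objective links Cardiac Compass-guided optimisation to activity, the decision rules in section 7 refer to CIED activity, and section 4.2 describes the wristband data as kept for later analysis. Against this, the fourth objective uses wristband activity within this study. No passage settles it. The two sources are not interchangeable: the wristband has no data before enrolment, and section 7 sets no minimum wear.

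**Step 3: what would baseline adjustment gain for walk distance and KCCQ?** The plan gives no figure to reproduce here.

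Inputs:
- About 30 enrolled, 10% dropout (section 17), 2:1 allocation (section 4): 30 × 0.9 = 27 evaluable, 18 vs 9.
- Correlation ρ between the enrolment and 6-month values: not in the documents, so assumed at 0.5 to 0.9.
- Equal variances at both times: assumed.

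The variance of the group difference is proportional to 2(1 − ρ) for raw change. For ANCOVA it is proportional to (1 − ρ²) × (1 + 1/(N − 4)), where the last factor is the expected inflation from chance baseline imbalance. The ratio is therefore

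ANCOVA / change = (1 + ρ)/2 × (1 + 1/(N − 4)),

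and the gain in effective sample size is 1/ratio − 1. At N = 27 the factor is 1 + 1/23 = 1.043:

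| ρ | Ratio | Gain |
|---|---|---|
| 0.5 | 0.783 | 28% |
| 0.6 | 0.835 | 20% |
| 0.7 | 0.887 | 13% |
| 0.8 | 0.939 | 6% |
| 0.9 | 0.991 | 1% |

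Break-even is where (1 + ρ)/2 = 23/24, so ρ = 0.917.

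Section 4 allows the month-6 visit to be remote, which could cost some walk tests; the number is not given. For illustration, at N = 18 (12 vs 6) the factor is 1 + 1/14 = 1.071. The gains are 24%, 17%, 10% and 4% at ρ = 0.5 to 0.8, with a loss of about 2% at 0.9. Break-even is where (1 + ρ)/2 = 14/15, so ρ = 0.867.

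**Step 4: scale.** With 9 vs 18 patients, 80% power at two-sided 0.05 requires a difference of (1.960 + 0.842) × √(1/9 + 1/18) = 1.14 SD by normal approximation. That is why these outcomes are better reported as estimates with intervals.

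**The case against.** The strongest defence is that discharge is leftover wording and the repair is editorial. Sections 4.2, 5 and 8 all describe patients around the time of implant, which suggests a design that followed them from there (an inference). For KCCQ the defence succeeds, because the Objectives and the schedule already supply the right anchor. For activity it does not, because no other section gives a baseline.

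A reader might infer that the activity outcome cannot be computed at all. The documents do not support that. The outcome ends at study month 6, and on the implant reading it could be computed if the ICD holds the stored data. The accurate statement is that the baseline is undefined.

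A reader might also infer that a month-1 baseline would be seriously contaminated by the intervention. The documents do not support that either. The first monthly virtual visit is scheduled at 1 month ± 7 days, so most of month 1 normally precedes it. The schedule table also marks a virtual visit at enrolment, so some overlap cannot be excluded. It is enough to state that month 1 follows randomisation.

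On analysis, it can fairly be said that a comparison of mean change is valid under randomisation, and that the ANCOVA gain rests on correlations the documents do not give. Both points stand. The gain disappears at high correlation, so ANCOVA is a likely improvement, not the correction of an invalid method.

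**Conclusion.** The point holds and is minor. Two secondary outcomes are timed from an event the trial does not define. For KCCQ this is an internal contradiction that a change of wording removes. For activity it leaves the baseline undefined, with the source unnamed as well. Section 17 is silent on the analysis of activity, KCCQ and walk distance.

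At 27 evaluable patients, ANCOVA on walk distance and KCCQ would be worth between about 28% (ρ = 0.5) and 1% (ρ = 0.9) in effective sample size over raw change. There is a small loss above about 0.92, or above about 0.87 if only 18 are evaluable. These figures rest on assumed correlations and equal variances. No precision gain is claimed for activity.

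**What to change.** 1. In the secondary outcomes of section 4, replace discharge with enrolment for both activity and KCCQ, so that KCCQ matches the Objectives.
2. Name one activity source in advance. If the ICD is chosen and stored data can be retrieved, use a fixed pre-randomisation window as baseline. Otherwise keep percentage change from month 1, state that month 1 is after randomisation, and do not use it as an ANCOVA covariate. If the wristband is chosen, also state what counts as a valid day of wear. Add to section 17 how the percentage change will be compared between groups.
3. Add to section 17 that 6-month walk distance and KCCQ are analysed by ANCOVA with the enrolment value as covariate, reporting the adjusted difference with a 95% CI, as unpowered secondary outcomes.

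The cost is a few lines of text, with no new visits or tests. The statistical downside of ANCOVA is the expected variance inflation from chance baseline imbalance, about 4% at 27 evaluable patients and 7% at 18, already counted in the gains above. The one thing to find out first is whether pre-enrolment ICD activity can be retrieved.
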